8.3.3. General Study Instructions

- Avoid extended periods of sun exposure and use of tanning beds and sunless tanning products for the duration of the study. Extra care should be taken to wear protective clothing, sunscreen, and accessories (such as sunglasses, hat, parasol) and avoid sun exposure from 10 AM to 3 PM.
- Do not use any topical skincare products on the assigned test areas including the affected areas (such as body wash, lotion, cream, oil, ointment), other than the provided study products, for the duration of the study.
- If the affected area is on the face, continue use of all regular brands of color cosmetics, makeup remover, and shaving products if used.
- Do not start using any new skincare or body care products other than the provided study products.

9. STUDY PROCEDURES

There will be 4 visits during the course of the study as illustrated in Table 1:

1. Visit 1 – Day 0 (screening/baseline)
2. Visit 2 – Week 2 (follow-up)
3. Visit 3 – Week 4 (follow-up)
4. Visit 4 – Week 8 (end of study or EOS)

Table 1. Study Visit and Assessments

Procedure	Visit 1	Visit 2	Visit 3	Visit 4
	D0	2 weeks after Baseline (± 3 days)	4 weeks after Baseline (± 5 days)	8 weeks after Baseline (± 5 days)
	Screening / Baseline	Follow-up	Follow-up	EOS
Informed consent	X			
Demographic	X			
Inclusion and exclusion criteria	X			
Concomitant medications	X	X	X	X
Lesion photography 
 Digital photography Macroscopic imaging¹ Capacitance imaging¹ 	X	X	X	X
Investigator clinical grading	X	X	X	X
Subjective tolerability assessment	X	X	X	X
Quality of Life questionnaire	X			X
Self-assessment questionnaire		X	X	X
Adverse events reporting		X	X	X
Study products	W/D	I/W	I/W	I/W/C
Subject diaries	D	C/R/D	C/R/D	C/R

For study products and daily diaries: D=Distribute, C=Collect, R=Review, W=Weigh, and I=Inspect (visually).

¹Performed at Site 2 only (n = 20-25).

9.1 Visit Examinations

9.1.1. Visit 1 (Screening / Baseline / Day 0)

Screening and Baseline visit can be combined if subject meets eligibility criteria. The following screening assessments will be performed:

- Obtain ICF and HIPAA form prior to conducting any study specific activity.

Note: Prior to beginning of any study related activities, subjects will be informed about the purpose and nature of the study, the expected post-treatment events, and the potential risks involved with the treatments. Once subjects have completed reading, they will be interviewed to ensure their understanding of the aforementioned forms and be given the

opportunity to ask any study related questions. Subjects declining to sign any of the forms will be dismissed from the study.

- Assess eligibility: review inclusion/exclusion criteria. Subjects failing to meet criteria will be dismissed from the study.
- Record the subject's demographic information, medical history, and concomitant medications.
- Female subjects will need to perform UPT to confirm childbearing potential. The test result must be negative for study qualification.

Once the subject is deemed eligible by the Investigator, the following procedures should be completed:

- Randomize the subject based on the predetermined computer-generated randomization.
- Obtain pre-treatment digital photography of psoriasis lesions, as described in Section 10.2.1, if subject consents.
 - For Site 2 only, perform additional photography (macroscopic, capacitance) of the lesions, as described in Section 10.2.2, 10.2.3.
- Perform investigator clinical grading as described in Section 10.1.
- Perform tolerability assessment as described in Section 11.1.
- Perform QoL questionnaire as described in 10.3.1.
- Dispense study products and diary. Instruct subjects on study product application and diary completion. Remind subjects to bring the study products and diary to the next clinic visit.
- Schedule the next follow-up Visit 2 (Week 2 \pm 3 days).

9.1.2. Visit 2 (Week 2 \pm 3 days)

- Confirm the subject's concomitant medications.
- Collect, weight, and redistribute the study products.
- Collect, review, and distribute the diary.
- Interview subjects regarding any AEs that have occurred since starting study product application.
- Obtain digital photography of psoriasis lesions, as described in Section 10.2.1, if subject consents.
 - For Site 2 only, perform additional photography (macroscopic, capacitance) of the lesions, as described in Section 10.2.2, 10.2.3.
- Perform investigator clinical grading as described in Section 10.1.
- Perform tolerability assessment as described in Section 11.1.
- Perform self-assessment questionnaire as described in Section 10.3.2.
- Schedule the next follow-up Visit 3 (Week 4 \pm 5 days).

9.1.3. Visit 3 (Week 4 \pm 5 days)

- Confirm the subject's concomitant medications.
- Collect, weight, and redistribute the study products.

Protocol GLI.04.US.SL.035

CONFIDENTIAL

- Collect, review, and distribute the diary.
- Interview subjects regarding any AEs that have occurred since the last visit.
- Obtain digital photography of psoriasis lesions, as described in Section 10.2.1, if subject consents.
 - For Site 2 only, perform additional photography (macroscopic, capacitance) of the lesions, as described in Section 10.2.2, 10.2.3.
- Perform investigator clinical grading as described in Section 10.1.
- Perform tolerability assessment as described in Section 11.1.
- Perform self-assessment questionnaire as described in Section 10.3.2.
- Schedule the next follow-up Visit 4 (Week 8 \pm 5 days).

9.1.4. Visit 4 (Week 8 \pm 5 days)

- Confirm the subject's concomitant medications.
- Collect and weight the study products.
- Collect and review the diary.
- Interview subjects regarding any AEs that have occurred since the last visit.
- Obtain digital photography of psoriasis lesions, as described in Section 10.2.1, if subject consents.
 - For Site 2 only, perform additional photography (macroscopic, capacitance) of the lesions, as described in Section 10.2.2, 10.2.3.
- Perform investigator clinical grading as described in Section 10.1.
- Perform tolerability assessment as described in Section 11.1.
- Perform QoL questionnaire as described in 10.3.1.
- Perform self-assessment questionnaire as described in Section 10.3.2.

9.2 Discontinued Subjects

Any subject is free to discontinue his/her participation in this study at any time and for whatever reason, specified or unspecified, and without prejudice.

An Investigator may decide to discontinue a subject from the study for safety reasons or when it is in the best interest of the subject. Galderma Laboratories, L.P. may also decide to prematurely terminate or suspend the study or the participation of a subject in the study. All data gathered on the subject prior to termination should be made available to Galderma Laboratories, L.P.

Criteria for the discontinuation of a subject during the study will include the following:

- Adverse Event
- Lack of Effect
- Pregnancy
- Subject Request
- Protocol Violation
- Lost to Follow-up
- Any unmanageable factor, in the Investigator's opinion, that may significantly interfere with the protocol or interpretation of results.

Protocol Version 02: 29 January 2024

This document contains confidential, proprietary information.

Protocol GLI.04.US.SL.035

CONFIDENTIAL

The reason and date for withdrawal should be documented in the subject's source documents and CRFs. When possible, an explanatory comment should be added to further explain the reason for the withdrawal. If withdrawal of a subject occurs during a regular study visit, the CRF for that specific visit shall be completed as far as possible.

If a subject is withdrawn from the study, all data collected until the time of withdrawal will be used in the analyses. Subjects who receive study products and are withdrawn or discontinued from the study will not be replaced. For AEs still ongoing at the time of withdrawal, see Section 11.

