10.3 Subject Questionnaire

10.3.1. Quality of Life Questionnaire

Subjects will be asked about their life quality by completing a QoL questionnaire at Baseline and Week 8, as described in Appendix II.

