11.5 Collection, Management and Reporting Procedures

The period of collection of adverse events starts from the time of signature of the Informed Consent Form (ICF) by the subject until the end of the subject's participation in the clinical study.

If a Serious Adverse Event (SAE) is on-going at the final clinical trial visit, it should be followed by the Investigator until it has resolved or has reached a stable condition.

After the subject completes the clinical study, the Investigator should also inform the Sponsor (see Sponsor's contact details below) if he/she becomes aware of an SAE involving a subject who has participated in the clinical study.

At each post enrollment visit, the Investigator will question the subject about AEs using an open non persuasive question to elicit reporting of AEs, for example "*Have you noticed any change in your health since the last visit?*" Direct questioning and examination will be performed when appropriate.

The Investigator will obtain and maintain in the subject's files all pertinent medical records, and (if applicable) information and medical judgment from colleagues who assisted in the treatment and follow-up of the subject. If necessary, the Investigator will contact the subject's personal physician or hospital staff to obtain further details.

As a minimum, Investigators are requested to report in the Case Report Form (CRF) and in the report all related adverse events (i.e., cosmetic adverse events) and all Serious Adverse Events, whether related or not.

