11.6 Pregnancy

Pregnancy itself is not to be considered as an adverse event. If a pregnancy occurs during the clinical trial, **the product application should be stopped immediately**, the subject should be withdrawn from the clinical study and Sponsor's representative (see Sponsor's contact details above) should be informed **within 24 hours**.

Pregnancy must be recorded as a reason for discontinuation in the exit form of the CRF.

No specific follow-up of pregnancy is required, except if it is a regulatory requirement in the country(ies) where the clinical trial is conducted.

Protocol GLI.04.US.SL.035

CONFIDENTIAL

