14.4 Data Management

A double-entry method will be used to enter data captured on paper records into a spreadsheet database to ensure accurate data transfer, and any missing data and/or inconsistencies will be identified and corrected.

The self-assessment questionnaire will be completed by subjects electronically using HIPAA-compliant SurveyMonkey online survey software. Paper questionnaires may be completed if needed.

All images taken from the study will be saved and shared to the Sponsor via a data-protected platform.

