I love how soft my skin feels					
The skin lesions have been consistently hydrated since using this moisturizer					
This moisturizer helps smoothen out the rough, scaly lesions					

	Yes	No
I would recommend the cleanser to my family and friend		
I would recommend the moisturizer to my family and friend		
I would recommend the product regimen to my family and friend		
I would purchase the cleanser		
I would purchase the moisturizer		
I would purchase the product regimen		

Protocol GLI.04.US.SL.035

CONFIDENTIAL

Testimonials (please provide any comments on your experience, study products, satisfaction/dissatisfaction, or anything related to this study)

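### With no early-termination assessment, subjects who leave before Week 8 supply no DLQI change and no end-of-study satisfaction answers, so these secondary results come from completers only

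*Combined protocol and SAP*

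**What the plan says.** **At withdrawal.** Section 9.2 (Discontinued Subjects) states: "If withdrawal of a subject occurs during a regular study visit, the CRF for that specific visit shall be completed as far as possible". It also says "The reason and date for withdrawal should be documented", with a comment when possible, and that "all data collected until the time of withdrawal will be used in the analyses". Withdrawn subjects who received product are not replaced. Section 11.6 mentions a CRF exit form: "Pregnancy must be recorded as a reason for discontinuation in the exit form of the CRF". Section 11.5 collects adverse events from consent "until the end of the subject's participation in the clinical study".

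**Schedule.** Table 1 and Section 9.1 list four visits (Baseline, Weeks 2, 4 and 8) and no early-termination visit. Section 10.3.1 has subjects "completing a QoL questionnaire at Baseline and Week 8". The self-assessment questionnaire is given at Weeks 2, 4 and 8, but Appendix III has a different item list at each visit. The six Yes/No recommend and purchase items, such as "I would purchase the product regimen", and the favorite-regimen item appear only at Week 8.

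**Analysis.** Section 4.1 makes quality of life at end of study against Baseline, and satisfaction at each follow-up visit, the two secondary objectives. Section 12.2 makes ITT the primary population. Section 12.4 tests the QoL change by Wilcoxon signed-rank test, and each questionnaire item without a baseline by a binomial (sign) test of favorable against unfavorable answers. Section 12.1 sets a two-sided 5% level. No missing-data method is stated.

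**The concern.** Section 9.2 commits to using all data up to withdrawal. For DLQI change and the Week 8 items that commitment is empty for anyone who leaves early, because nothing usable has been asked by then. Withdrawing at the Week 2 or Week 4 visit does not help: completing that visit's CRF includes neither the DLQI nor the Week 8 items.

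Section 9.2 lists adverse event and lack of effect among the reasons for discontinuation. Subjects leaving for those reasons would plausibly answer less favorably than those who stay. If so, the observed DLQI improvement and the Week 8 favorable percentages are too optimistic, and a sign test close to its threshold could reach significance because of who was left to answer. Section 4.2 predicts statistical significance for both instruments. The true answers cannot be obtained after the study, whatever the analysis.

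**Working it through.** The plan gives no dropout rate and no derivation of its 40–50 completers, so there is no planned figure to reproduce. The check has a documentary part and an illustrative part.

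**1. What each subject can contribute** (Table 1, Sections 9.1 and 9.2, Appendix III)

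| Subject leaves | DLQI values | DLQI change | Recommend/purchase answers | Earlier self-assessment items |
|---|---|---|---|---|
| Before Week 2 | Baseline only (1 of 2) | none | 0 of 6 | none |
| At or after Week 2, before Week 4 | 1 of 2 | none | 0 of 6 | Week 2 |
| At or after Week 4, before Week 8 | 1 of 2 | none | 0 of 6 | Weeks 2 and 4 |
| During the Week 8 visit | up to 2 of 2 | possible | up to 6 of 6 | Weeks 2 and 4 |

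The last row follows from the rule on withdrawal during a regular visit. Appendix III has 10 agree/disagree items and 6 Yes/No items at Week 8, so 10 + 6 = 16 items are exposed, each with its own test.

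**2. How many could be missing.** Enrolled = completers / (1 − d), rounded up, with d **assumed**:

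| Assumed d | 40 completers: enrolled (missing) | 50 completers: enrolled (missing) |
|---|---|---|
| 5% | 43 (3) | 53 (3) |
| 10% | 45 (5) | 56 (6) |
| 15% | 48 (8) | 59 (9) |
| 20% | 50 (10) | 63 (13) |

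**3. Effect on a sign test.** For k favorable of n, with X ~ Binomial(n, 0.5), the two-sided exact p = 2·P(X ≥ k). Take a Yes/No item at Week 8 and add hypothetical answers from leavers:

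| Completers | Added answers | Total | p |
|---|---|---|---|
| 28/40 (70%) | none | 28/40 | 0.017 |
| 28/40 | 2 unfavorable | 28/42 | 0.044 |
| 28/40 | 3 unfavorable | 28/43 | 0.066 |
| 28/40 | 5 unfavorable | 28/45 (62%) | 0.135 |
| 28/40 | 3 unfavorable, 2 favorable | 30/45 | 0.036 |
| 30/40 | 5 unfavorable | 30/45 | 0.036 |
| 32/40 | 5 unfavorable | 32/45 | 0.007 |

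**4. At the threshold.** The smallest significant count among 40 is 27 (67.5%, p = 0.038). If all leavers at the assumed 5, 10, 15 and 20% dropout answered unfavorably, p becomes 0.126, 0.233, 0.471 and 0.672. Among 50 the smallest count is 33 (66%, p = 0.033), which becomes 0.098, 0.229, 0.435 and 0.801.

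A result near the threshold is therefore fragile to three unfavorable leavers, while a clear majority such as 32/40 withstands five.

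**The case against.** A reader might infer that nothing is collected when a subject withdraws. The documents do not support that. Reason and date are recorded for every withdrawal, an exit form exists, adverse events are collected until participation ends, and all earlier visit data are kept. Whether someone left for an adverse event or lack of effect will be known.

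A reader might also infer that leavers contribute nothing to quality of life or satisfaction. That too goes beyond the text. They have a Baseline DLQI. The satisfaction objective covers each follow-up visit, and anyone who reaches Week 2 answers items on irritation, drying, softness and hydration. Several Week 8 themes (softness, hydration, healthier look) have close, though not identical, earlier counterparts. BSA, TLSS, PGA and tolerability are graded at every follow-up visit.

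On size, a reversed sign test needs a result near the threshold and mostly negative leavers. Section 9.2 also lists reasons, such as pregnancy and loss to follow-up, that need not reflect dissatisfaction. A worst-case analysis could bound the bias without new data.

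Exit data have limits as well. The DLQI asks about the last week, so a score at an early exit does not measure the same thing as a Week 8 score. Section 14.4 provides for electronic completion of the self-assessment only.

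All of this stands, and it confines the point to DLQI change and the Week 8 items. None of it supplies a post-Baseline DLQI or a Week 8 answer for an early leaver, and a bound shows how far the result could move without showing where it lies.

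**Conclusion.** The gap is real but limited. No early-termination assessment is specified, so DLQI change and the Week 8 satisfaction items are in effect completer analyses, although ITT is the primary population. A favorable bias is plausible if leavers are less satisfied; the documents cannot show that they will be.

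The magnitude is illustrative. It rests on assumed numbers of leavers and assumed answers. It would be tempting to conclude that the positive-perception finding would reverse. The figures do not support this as a general statement: 28/40 loses significance with three added unfavorable answers but not with two, and 32/40 keeps it with five. The favorable percentage falls in every case where the leavers' answers are less favorable than the completers'.

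This is an inexpensive improvement to secondary endpoints, worth making because the missing answers cannot be recovered later. It does not undermine the primary assessments.

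**What to change.** **Collection.** Add an early-termination column to Table 1 and a sentence to Section 9.2: at withdrawal, unless the subject refuses, the Visit 4 assessments are performed. If the subject will not attend, at minimum the DLQI and Week 8 questionnaire are completed remotely or on paper. The self-assessment route already exists ("The self-assessment questionnaire will be completed by subjects electronically using HIPAA-compliant SurveyMonkey online survey software", with paper as a fallback). Remote DLQI completion would have to be added; Appendix II puts the usual completion time at one or two minutes.

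**Analysis.** Keep the Week 8 analysis as planned. In Section 12.4 add (a) a sensitivity analysis that includes exit responses, reporting when each was obtained, and (b) for the Week 8 items, a bound that counts remaining non-responders as unfavorable. State the denominator for both, because Section 12.2 ties ITT to completing at least one follow-up visit and so leaves out anyone who exits before Week 2.

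**Cost.** A small amendment, and one short visit or form per withdrawal: 3 to 13 subjects under the assumed 5–20% dropout. The downsides are that exit responses come at varying times, subjects lost to follow-up stay missing, and the reported satisfaction figures may fall slightly.

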10. EFFICACY ASSESSMENTS

The methods for collecting effectiveness data are described in this section. To minimize inter-observer variability, every effort should be made to ensure that preferably the same individual who makes the initial baseline assessments completes all corresponding follow-up evaluations.

Prior to participating in the following procedures, clinic personnel will ensure that subjects have clean test areas and have not applied any topical products. Subjects will acclimate to ambient conditions within the clinic with test areas exposed for at least 15 minutes. The designated rooms will be maintained at a temperature of 68-75 °F and the relative humidity will range from 35%-65%.

[figure not shown]
The methods for collecting efficacy data are:

- Clinical Grading by Investigator
- Lesion Photography
- Subject Questionnaire

10.1 Clinical Grading by Investigator

10.1.1. Body Surface Area (BSA)

Investigator will perform clinical grading of BSA at Baseline, Week 2, 4, and 8. BSA is a measure of how much skin is impacted by psoriasis using the following measurement.⁷ One handprint is equal approximately to 1% of BSA.

Figure 2. BSA Grading

© 2020 National Psoriasis Foundation

10.1.2. Target Lesion Severity Score (TLSS)

Investigator will perform clinical grading of TLSS, at Baseline, Week 2, 4, and 8. The target lesion parameters will be assessed using the following numerical scales.⁸ Odd scores may be used as necessary to more accurately describe the skin condition.

Table 2. TLSS Grading

Parameter	Score	Definition
Erythema	0	No evidence of erythema
	2	Pink coloration
	4	Red coloration
	6	Very red coloration
	8	Extreme red (deep red) coloration
Induration	0	No evidence of plaque above normal skin level
	2	Slight definite elevation above normal skin level
	4	Moderate elevation above normal skin level
	6	Marked elevation above normal skin level
	8	Very marked elevation above normal skin level
Scaling	0	No evidence of scaling on the lesions
	2	Mild mainly fine scales, some lesions at least partially covered
	4	Moderate somewhat coarser scale, most lesions at least partially covered
	6	Severe coarse thick scales, virtually all lesions covered with rough surface
	8	Very severe coarse very thick scales, all lesions covered with rough surface

TLSS score is calculated as cumulative total of all 3 parameters, which a maximum score of 24 (8 x 3).

10.1.3. Physician Global Assessment (PGA)

Investigator will perform clinical grading of PGA, at Baseline, Week 2, 4, and 8. The overall severity will be assessed using the following numerical scales.⁸

Table 3. PGA Grading

Score	Severity	Description
0	Clear	No signs of psoriasis (hypo/hyperpigmentation allowed). No plaque elevation. No Scaling. Erythema +/- (hyperpigmentation). Diffuse faint pink or red (macular).
1	Almost clear	Plaque elevation +/- (possible but difficult to ascertain elevation). Scaling +/- (surface dryness with some white discoloration). Erythema up to moderate (up to definite red coloration).
2	Mild	Plaque elevation slight (slight but definite, edges indistinct but sloped). Scaling fine (fine with partial or mostly covering lesions). Erythema up to moderate (up to definite red coloration).
3	Moderate	Plaque elevation moderate (moderate elevation with rough or sloped edges). Scaling coarse (coarse scale covering most or all of the lesions). Erythema moderate (definite red coloration).
4	Severe	Plaque elevation marked (marked with hard or sharp edges). Scaling coarse (coarse nontenacious scale predominates covering most of all lesions). Erythema severe (very bright red coloration).
5	Very severe	Plaque elevation very marked (very marked with hard sharp edges). Scaling very coarse (coarse thick tenacious scale covering most of all lesions with rough surface). Erythema very severe (extreme dusky to deep red coloration).

